6.3.2 Derivation or calculation of outcome variable

Previous text:

Symptom control rate is calculated as the proportion of patients whose symptom controlled at the Week 8, 16 and 24 visits in maintenance treatment or follow-up phase. Controlled patients are defined as patients with all items ≤ 1 in A and C category of GerdQ.

Time to first relapse is defined as after 8 weeks / 2 weeks treatment, the time to the patients first come to see the investigator because of symptom recur, and need for treatment. The on-demand drugs in the 8 weeks treatment regimen group will be dispensed after the first relapse. The average time to first relapse in the two groups will be compared.

Symptom relief is defined as patients with no more than one day mild symptoms of GERD

during the previous 7 days. Symptom relief rate is calculated as the proportion of patients whose symptom relieved after 8 weeks and 2 weeks treatment.

Unscheduled hospital visit is calculated as the number of unscheduled hospital visit in 8 weeks treatment regimen and 2 weeks treatment regimen groups.

Patient satisfaction will be measured using a 7-point scale (completely satisfied-1; very satisfied-2; quite satisfied-3; satisfied-4; dissatisfied-5; very dissatisfied-6; completely dissatisfied-7). The patient will fill out the scale at Week 8, 16 and 24 visits in maintenance treatment or follow-up period. The proportion of patients satisfied (scores 1-4) or very satisfied (scores 1-2) will be calculated.

Revised text:

Success is defined as patients who relieved after 8 weeks or 2 weeks esomeprazole treatment, and also get symptom controlled after 24 weeks maintenance treatment/follow up period.

Symptom control rate is calculated as the proportion of patients whose symptom controlled at the Week 8, 16 and 24 visits in maintenance treatment or follow-up phase. Controlled patients are defined as patients with all items ≤ 1 in A and C category of GerdQ.

Time to first relapse is defined as after 8 weeks / 2 weeks treatment, the time to the patients first come to see the investigator because of symptom recur, and need for treatment. The on-demand drugs in the 8 weeks treatment regimen group will be dispensed after the first relapse. The average time to first relapse in the two groups will be compared.

Symptom relief is defined as patients with no more than one day mild symptoms of GERD during the previous 7 days. Symptom relief rate is calculated as the proportion of patients whose symptom relieved after 8 weeks and 2 weeks treatment.

Unscheduled hospital visit is calculated as the number of unscheduled hospital visit in 8 weeks treatment regimen and 2 weeks treatment regimen groups.

Patient satisfaction will be measured using a 7-point scale (completely satisfied-1; very satisfied-2; quite satisfied-3; satisfied-4; dissatisfied-5; very dissatisfied-6; completely dissatisfied-7). The patient will fill out the scale at Week 8, 16 and 24 visits in maintenance treatment or follow-up period. The proportion of patients satisfied (scores 1-4) or very satisfied (scores 1-2) will be calculated.

Reason for Amendment:

Relief rate is to evaluate the efficacy of initial 8 week or 2 week treatment, and symptom control rate is to evaluate the efficacy of 24 weeks maintenance treatment/follow up period. Now success rate is added to evaluate the efficacy of whole treatment regimen, it is the combination of relief and control.

Section of protocol affected:

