	Week -1	Week 0	Week 2	Week 8 ^b	
Inclusion & exclusion criteria	X	X			
Informed Consent	X				
Randomisation		X			
Medical history	X				
Demographic data	X				
Urine HCG ^c		X			
Physical examination	X				
Vital signs	X				
Laboratory measurement ^d	X				
Hp infection ^{d,e}	X				
Concomitant medication	X	X	X	X	
Drug dispensing		X	X ^b		
Drug accountability			X	X	
GerdQ assessment	X				
SAEs/ DAEs ^f assessment	X ^g →	X→	X→	X→	

^a Once informed consent given, baseline procedures may be completed within 1 week prior to treatment start.

^b Just for patients in 8 weeks treatment regimen group.

- ^c For women of child-bearing potential, a pregnancy test with a negative result must have been made before study.
- ^d Laboratory test results in the previous 2 weeks are acceptable, no need to repeat laboratory test at Visit 1.
- ^e Hp infection status diagnosed by ¹³C-urea breath test (UBT), rapid urease test or pathologic test.
- ^f Only SAEs and DAEs will be collected.
- ^g SAEs will be captured from time of signature of informed consent. DAEs will be captured from time of first dose of IP.

Table 2 Study Plan 2 (Visits in 24 weeks on-demand maintenance treatment/ follow-up period)

	24-week Maintenance treatment/ follow up			
	5 Week 8 ± 3d	6 Week 16 ± 3d	7 ^a Week 24 ± 3d	Unscheduled ^b
Concomitant medication	X	X	X	X
Drug dispensing	X ^c	X ^c		X
Drug accountability	X	X	X	X
GerdQ assessment	X	X	X	
Patient satisfaction	X	X	X	
SAEs/ DAEs ^d assessment	X→	X→	X	X

- ^a If a patient discontinues from the study prior to the Week 24 visit (study completion), every effort should be made to have the patient return for a clinic visit at the time of, or soon after discontinuation to complete all Final Visit procedures.
- ^b This includes all unscheduled visits carried out during maintenance treatment/ follow up period due to symptom recur and extra treatment needed. Total unscheduled visits will be compared between two treatment group.
- ^c Just for patients in 8 weeks treatment regimen group, only after the first relapse happened. If patients in CG group have symptom relapse at a scheduled visit, drugs will also be dispensed to them.
- ^d Only SAEs and DAEs will be collected.

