5.2.1 Procedures for randomisation

The randomization will be performed by a computer equally for the two treatment regimens. Each centre will be provided with sealed treatment code envelopes corresponding to a list of patient randomization numbers. Randomization numbers will be assigned strictly sequentially as subjects become eligible for randomization. When a subject is allocated to a specified randomization number, the corresponding code envelope will be opened to identify the allocated treatment regimen (8 weeks or 2 weeks treatment regimen).

5.3 Procedures for handling subjects incorrectly enrolled or randomised or initiated on investigational product

Subjects who fail to meet the inclusion/exclusion criteria should not, under any circumstances, be enrolled or randomised. There can be no exceptions to this rule.

Where subjects that do not meet the selection criteria are randomised in error or incorrectly started on treatment, or where subjects subsequently fail to meet the study criteria post initiation, a discussion should occur between the AstraZeneca Study Delivery Team Physician and the Investigator regarding whether to continue or discontinue the subject from treatment.

The AstraZeneca Study Delivery Team Physician is to ensure all such decisions are appropriately documented. In situations where an agreement cannot be reached, the subject should have their study therapy stopped.

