12.2 Methods of statistical analyses

In general, the descriptive statistics (number, mean, median, standard deviation, minimum and maximum) will be performed for continuous variables. The frequency tables (number and percentage of subjects) will be performed for categorical variables. All statistical tests will be two-sided with the 5% level of significance.

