12.2.1 Analyses of efficacy endpoints

Analysis on efficacy endpoints will be performed for ITT, MITT and PP population.

Fisher's exact test will be used to assess statistical difference in symptom control rate in 8 weeks treatment regimen group, compared with 2 weeks treatment regimen group. Differences between treatment groups in the proportion of patients very satisfied (scores 1-2) and satisfied (scores 1-4) will also be analyzed using Fisher's exact test. Symptom relief after 8 weeks or 2 weeks treatment will be summarized with number and percentage of patients in each category.

The number of unscheduled hospital visit was compared between treatments using two-sample t-test. Kaplan-Meier method will be used to assess time to first relapse and a log-rank test to provide a comparison of treatment groups.

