12.3 Determination of sample size

The primary objective of this study is to compare the symptom control rate in 8 weeks treatment regimen group, and 2 weeks treatment regimen group after 24 weeks maintenance treatment/ follow-up. Since we do not have previous data for the symptom control rate in the two treatment regimens, the sample size was calculated based on clinical experience. With a total of 170 evaluable patients, 85 in the 8 weeks treatment regimen group and 85 in the 2 weeks treatment regimen group, the power would be over 80% to detect a difference of 20% in symptom control rate between two treatment groups at two-sided 0.05 significance level using Fisher exact test, assuming the symptom control rate is around 66% in 2 weeks treatment regimen group and 86% in 8 weeks treatment regimen group (based on data from BU-NEG-0005 study). Considering the PPI response rate is around 70% and drop off rate will be 20%, around 300 patients are needed to be randomised.

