To compare the success rate between 8 weeks esomeprazole treatment regimen group and 2 weeks esomeprazole treatment regimen group in co-diagnosed NERD and chronic gastritis patients.	The success rate in 8 weeks treatment regimen group, compared with 2 weeks treatment regimen group after 24 weeks on-demand maintenance treatment/ follow up. Success is defined as patients who relieved after 8 weeks or 2 weeks esomeprazole treatment, and also get symptom controlled after 24 weeks maintenance treatment/follow up period. (ITT, ITT-PP)	Summary statistics (number and percentage of patients in each category). Treatment group comparison of proportion of patients succeeded, Fisher's exact test.
To assess time to first relapse.	Time to first relapse, defined as the time to the patients first come to see the investigator because of symptom recur and need for treatment after 8 weeks or 2 weeks treatment in the two treatment regimen groups. (MITT and MITT-PP)	Median and percentiles of time to relapse, if appropriate. Treatment group comparison using Log-Rank test.

Objective	Summary variables for analysis (including timepoint and population)	Statistical analysis methods or presentation of data
To assess symptom control rate after 8 /16 weeks visits in 24 weeks maintenance treatment/follow up period, as evaluated by GerdQ.	The symptom control rate after 8 and 16 weeks on-demand maintenance treatment/ follow up in the two different treatment regimen groups. Controlled patients are defined as patients with all items ≤ 1 in A and C category of GerdQ. (MITT and MITT-PP)	Summary statistics (number and percentage of patients in each category). Treatment group comparison of proportion of patients controlled, Fisher's exact test.
To assess the symptom relief rate after 8 weeks or 2 weeks esomeprazole treatment in the two different treatment regimen groups.	The symptom relief rate after 8 weeks or 2 weeks treatment in the two treatment regimen groups (Symptoms relief are defined as no more than one day with mild symptoms of GERD during the previous 7 days). (ITT,ITT- PP)	Summary statistics (number and percentage of patients in each category).

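### Time to first relapse: section 6.3.2 compares averages while the plan elsewhere uses log-rank, and no single event rule covers relapses found at scheduled visits in both arms

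*Protocol*

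**What the plan says.** **Comparison.** Protocol section 6.3.2, in both the main text and the revised text of Amendment 1, says: "The average time to first relapse in the two groups will be compared". Section 12.2.1 says: "Kaplan-Meier method will be used to assess time to first relapse and a log-rank test to provide a comparison of treatment groups". The amended endpoint table in section 6.3.1 gives median and percentiles where appropriate, with a log-rank test. The synopsis also names Kaplan-Meier.

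**Event.** The amended endpoint table gives: "Time to first relapse, defined as the time to the patients first come to see the investigator because of symptom recur", with a need for treatment added. Section 6.3.2 has the same definition.

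**Scheduled visits.** Follow-up visits are set at Weeks 8, 16 and 24 (Visits 5, 6 and 7). Table 2 footnote c reserves dispensing at Visits 5 and 6 for the 8-week group after a first relapse, then adds: "If patients in CG group have symptom relapse at a scheduled visit, drugs will also be dispensed to them". Section 5.5.2 equates the 8-week group's relapse time with the first dispensing in the maintenance phase, and in the same sentence describes it as the patient going to consult. Section 5.7.1 lists dispensing at Visits 5 and 6 for the 8-week group only.

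**The concern.** Two things are fixed badly in the stated text.

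First, section 11.1 names section 6.3.2 as the place where efficacy variables are derived, and it points to a different comparison from the statistical methods section. With follow-up ending at 24 weeks, a patient who does not relapse has no relapse time. An average then depends on what is done with those patients, and the protocol does not say.

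Second, whether a relapse found at a scheduled visit counts depends on which passage is followed, and the passages are not worded alike for the two arms. The trial is open-label and the event depends on the patient's decision to consult. If one arm's scheduled-visit relapses count and the other's do not, the curves differ partly because of the counting rule. That could hide a real difference or exaggerate one.

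**Working it through.** **1. The plan's own figure.** The protocol gives no power or event figure for this endpoint. Its only calculation is for the primary endpoint: "With a total of 170 evaluable patients, 85 in the 8 weeks treatment regimen group and 85 in the 2 weeks treatment regimen group", for which it says "the power would be over 80% to detect a difference of 20% in symptom control rate between two treatment groups". Inputs are 66% and 86% control, two-sided 5% and equal allocation. Exact enumeration of Fisher's test gives power 0.838, which agrees. The number to randomise is 170 / (0.70 × 0.80) = 303.6, against about 300 stated. Nothing below changes this.

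**2. The passages side by side.** Take a patient whose recurrence is first noticed at the Week 8 or Week 16 scheduled visit and who is given drug there.

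- Definition in 6.3.1 and 6.3.2: the visit was made because it was scheduled, so read literally there is no event, in either arm.
- Table 2 footnote c: in the CG group, taken here to be the 2-week group, this is called a relapse and drug is given. It does not say whether it is an endpoint event.
- Section 5.5.2: in the 8-week group, first maintenance dispensing is the relapse time, which would count it. The consulting condition in the same sentence could still leave it out.
- Section 5.7.1: the 2-week group is not listed for dispensing at these visits, contrary to footnote c.

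Three outcomes are therefore possible: the relapse is missed in both arms, only in the 2-week arm (5.5.2 applied to one arm, the literal definition to the other), or only in the 8-week arm (footnote c taken as counting, the literal definition applied to the 8-week arm).

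**3. What each outcome could do.** Assumptions, because the documents give no figures:

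- 24-week relapse is 34% (2-week) and 14% (8-week), the complements of the assumed control rates.
- Hazards are constant, with 85 patients per arm.
- The share of relapses left uncounted is 10%, 25% or 50%.

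True hazard ratio = ln(0.86)/ln(0.66) = 0.363. Expected events = 85 × (0.34 + 0.14) = 40.8. Schoenfeld power = Φ(√(events/4) × |ln HR| − 1.96) = Φ(3.19 × 1.013 − 1.96) = 0.90 with all relapses counted.

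With 25% lost in both arms and the hazard ratio held at 0.363, events are 30.6 and power is 0.80. With 25% lost only in the 2-week arm, its rate becomes 0.34 × 0.75 = 0.255, the apparent hazard ratio is ln(0.86)/ln(0.745) = 0.51, events are 33.6 and power is 0.49. With 25% lost only in the 8-week arm, its rate becomes 0.14 × 0.75 = 0.105, the apparent hazard ratio is ln(0.895)/ln(0.66) = 0.27, events are 37.8 and power is 0.98.

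| Share uncounted | Both arms: power | 2-week arm only: power (apparent HR) | 8-week arm only: power (apparent HR) |
|---|---|---|---|
| 10% | 0.87 | 0.78 (0.41) | 0.94 (0.32) |
| 25% | 0.80 | 0.49 (0.51) | 0.98 (0.27) |
| 50% | 0.63 | 0.08 (0.81) | >0.99 (0.17) |

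The last column is not a gain: the higher power comes from an exaggerated effect. A simulation of 2,000 trials gave log-rank power of 0.87 with all relapses counted. It gave 0.77 and 0.53 for 25% and 50% lost in both arms, and 0.49 and 0.09 when lost only in the 2-week arm.

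**The case against.** The strongest reply is that every passage naming a method for this endpoint names a survival method. The log-rank test is the only test named, and where the protocol wants a test of means, as for unscheduled visits, it says so. That stands. A reader might infer that the trial will test mean relapse times and so miss a real difference, or might compute an average among relapsers alone. The documents plan neither, so the sentence in 6.3.2 is a contradiction to remove and does not show that the analysis is wrong.

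It can also be said that no passage expressly excludes a relapse found at a scheduled visit, and that footnote c and section 5.5.2 lean towards counting it. That stands too: exclusion is one reading, and the direction of any bias is not known. Nor does Table 2 support treatment for relapse at all three scheduled visits, since it marks no dispensing at Visit 7. What the reply does not settle is which rule applies and whether it is the same in both arms.

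The relapse rates used above are borrowed. The synopsis says the control rates rest on a relapse rate from another study, but both arms are re-treated after relapse, so a patient who relapsed can still be controlled at Week 24. The table therefore shows direction and possible scale, not a forecast.

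A reader might go further and ask for an intention-to-treat analysis timed from randomisation with non-relief as an event. Events could then begin at Week 2 in one arm but only at Week 8 in the other, so the curves would separate mechanically. That analysis is not recommended.

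**Conclusion.** The point holds as an inconsistency in the stated text of a secondary endpoint. The sentence on averages conflicts with the log-rank plan, and the event rule conflicts across passages and is worded differently by arm. Its size cannot be fixed from the documents, because the share of relapses found at scheduled visits is not given. Under the stated assumptions and a 10% to 50% share, equal loss costs moderate power (0.87 down to 0.63, from 0.90). Unequal loss matters more: from 0.78 down to 0.08 if it falls on the 2-week arm, or an apparent hazard ratio of 0.32 down to 0.17 in place of 0.36 if it falls on the 8-week arm. The primary endpoint, its test and the sample size are unaffected.

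**What to change.** 1. Delete the sentence on average time from section 6.3.2, so that Kaplan-Meier and log-rank stand alone.
2. In sections 6.3.1 and 6.3.2, state one event rule for analysis in both arms: the first date on which study drug is dispensed for symptom recurrence, at any visit, scheduled or unscheduled. Since Table 2 marks no dispensing at Visit 7, say how a recurrence first found there is treated, alike in both arms.
3. Reconcile Table 2 footnote c, section 5.5.2 and section 5.7.1 on who is dispensed drug at scheduled visits. Which practice is right is for the sponsor to settle.

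The cost is a small change to the endpoint wording, to be made before database lock. Drug dispensing is already recorded at scheduled and unscheduled visits, so no new data are needed.

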12.1.1 Efficacy analysis set

Previous text:

Analysis on efficacy endpoints will be performed for intention to treat (ITT) population and modified intention to treat (MITT) population. ITT is defined as all randomized subjects who have taken at least one dose of trial treatment. MITT is defined as patients in ITT population whose symptoms relieved after 8 weeks or 2 weeks esomeprazole treatment. Efficacy analysis will also be repeated in per protocol (PP) population defined as all ITT subjects without significant protocol violations/deviations. Detailed criteria and identification of the Per Protocol population will be decided in the statistical analysis plan prior to database lock.

Revised text:

Analysis on efficacy endpoints will be performed for intention to treat (ITT) population, modified intention to treat (MITT) population and per protocol (PP) population, with MITT as the primary analysis population.

ITT is defined as all randomized subjects who have taken at least one dose of trial treatment. MITT is defined as patients in ITT population whose symptoms relieved after 8 weeks or 2 weeks esomeprazole treatment. Efficacy analysis will also be repeated in per protocol (PP) population including ITT-PP and MITT-PP population, defined as all subjects without significant protocol violations/deviations out of ITT and MITT population respectively. Detailed criteria and identification of the Per Protocol population will be decided in the statistical analysis plan prior to database lock.

Reason for Amendment:

Relief rate is to evaluate the efficacy of initial 8 week or 2 week treatment, and symptom control rate is to evaluate the efficacy of 24 weeks maintenance treatment/follow up period. Now success rate is added to evaluate the efficacy of whole treatment regimen, it is the combination of relief and control.

The calculation of relief rate and success rate should be based on ITT population, and symptom control rate on MITT population. Correspondingly, it will make more sense to differentiate PP population as ITT-PP and MITT-PP.

Persons who initiated the Amendment:

Study statistician

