5.4 Blinding and procedures for unblinding the study

Blinding was not performed in this study (reasons given in Section 3.2).

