5.5.2 Doses and treatment regimens

Patients will be randomized into below two groups at the Visit 2.

8 weeks treatment regimen group:

Patients will receive 8 weeks esomeprazole 20 mg qd treatment, if symptom relieved (defined as no more than one day with mild symptoms of GERD during the previous 7 days), they will receive another 24 weeks on-demand maintenance treatment. The first drug dispensing during maintenance phase is the time of first relapse, which is defined as patients' symptom recur, go to consult investigators and need treatment in the opinion of investigator. The following on-demand drugs will be dispensed at Visit 5 and 6 if the first relapse happened before Visit 5. Patients will be instructed to "Take one tablet daily if needed for relief of your reflux symptoms for at least 3-5 days. Stop taking the tablets when your symptom is adequately controlled."

During 24 weeks on-demand maintenance treatment period, 14 tablets esomeprazole will be dispensed at each scheduled visit. If it is not enough before next scheduled visit, patients can

go to the study center to get extra drugs. If they do not have symptoms recur, and just come to get on-demand drugs, it is not considered as unscheduled visit.

2 weeks treatment regimen group:

Patients will receive 2 weeks esomeprazole 20 mg qd treatment, if symptom relieved, they will enter 24 weeks follow-up period. During the followed up period, if the patients' symptom recur and need treatment in the opinion of investigator, they will be given another 2-week esomeprazole 20 mg qd recurrent treatment. There is no limitation for the times of recurrent treatment in the 24-week follow up period.

Study medication should be taken once daily in the morning with a glass of water.

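### The ITT set leaves out randomised patients who took no dose, although the open-label regimen is known before the first dose, so the one between-arm test assigned to ITT can lose patients by arm

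*Protocol*

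**What the plan says.** The amended section 12.1.1 fixes the set: "ITT is defined as all randomized subjects who have taken at least one dose of trial treatment". The synopsis has the same definition. Only the detailed per-protocol criteria are deferred to the statistical analysis plan, so the ITT definition is settled in the protocol itself.

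Section 5.4 states that "Blinding was not performed in this study". Under section 5.2.1, once a randomisation number is allocated, "the corresponding code envelope will be opened to identify the allocated treatment regimen". Section 5.5.2 places this at the second visit ("Patients will be randomized into below two groups at the Visit 2"), and Table 1 puts the first drug dispensing at that same Week 0 visit.

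Amendment 1 divides the endpoints between populations: "The calculation of relief rate and success rate should be based on ITT population, and symptom control rate on MITT population". In the amended table of section 6.3.1, the success rate (ITT and ITT-PP) carries a Fisher's exact test, described as "Treatment group comparison of proportion of patients succeeded". The two relief-rate variables are also on ITT but have summary statistics only. Every other efficacy variable is on MITT and MITT-PP. The primary analysis does not use ITT, since section 12.1.1 sets the efficacy populations "with MITT as the primary analysis population".

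**The concern.** Requiring one dose is usually defensible under blinding, because the decision to start cannot depend on an allocation nobody knows. That protection is absent here. Membership of the ITT set depends on behaviour after the arm has been disclosed.

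The regimens also look different to a patient. One lasts 32 weeks with on-demand tablets after relapse. The other lasts 26 weeks, with a repeat 2-week course each time the investigator judges that a recurrence needs treatment. The protocol's introduction itself describes overall symptom control after one or two weeks of treatment as poor. Refusal after allocation could therefore differ by arm, in either direction.

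Section 12.1 says efficacy is analysed by randomised treatment. That settles which arm a patient counts in, not whether the patient is counted.

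The success rate was added to evaluate the whole regimen. MITT already selects on relief after randomisation, so success in ITT is the one tested comparison that could preserve randomisation. If refusals differ by arm, the difference is biased and the result carries an ITT label it has not earned.

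**Working it through.** **The plan's own figure.** Section 12.3 assumes control rates of 66% and 86%, 85 evaluable patients per arm, and a two-sided 0.05 Fisher's exact test. Enumerating both binomial distributions gives power of 83.8%, which agrees with the stated figure of over 80%. Inflation for 70% response and 20% drop-off gives 170 / 0.70 / 0.80 = 303.6, or around 300 randomised. Neither figure depends on the ITT definition.

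**Inputs for the illustration.**
- Response 70%, control 86% (8-week) and 66% (2-week): section 12.3.
- About 150 patients per arm: synopsis.
- Number undosed, k: an assumption, because the protocol gives none. Values of 3, 5, 8 and 15 (2% to 10% of an arm) are shown, lost from one arm only.
- A never-dosed patient would count as a non-success: an assumption.

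**Success rate in all randomised patients.** Success = response × control.
- 8-week: 0.70 × 0.86 = 60.2%
- 2-week: 0.70 × 0.66 = 46.2%
- Difference: 14.0 points

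**Success rate with k undosed patients removed.** Observed rate = p × 150 / (150 − k).
- 2-week arm, k = 5, 8, 15: 0.462 × 150 / 145 = 47.8%; 0.462 × 150 / 142 = 48.8%; 0.462 × 150 / 135 = 51.3%
- 8-week arm, k = 8: 0.602 × 150 / 142 = 63.6%

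The table gives the resulting difference. The Fisher p-values use whole counts, 90/150 against 69/150, for which p = 0.021 when nobody is removed.

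| k undosed, one arm only | Lost from 2-week arm | Lost from 8-week arm |
|---|---|---|
| 3 | 13.1 points, p = 0.027 | 15.2 points, p = 0.010 |
| 5 | 12.4 points, p = 0.036 | 16.1 points, p = 0.007 |
| 8 | 11.4 points, p = 0.060 | 17.4 points, p = 0.003 |
| 15 | 8.9 points, p = 0.15 | 20.7 points, p = 0.0005 |

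**Type I error.** Suppose the true success rate in all randomised patients is 53% in both arms, close to the midpoint of 60.2% and 46.2%. Fisher's test rejects 4.3% of the time when nobody is removed. Removing 3, 5, 8 or 15 undosed non-successes from one arm raises this to 5.1%, 5.6%, 7.6% or 15.2%.

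**Small or balanced losses.** One or two undosed patients in one arm move the difference by about 0.3 to 0.8 points. Five in each arm give 0.602 × 150 / 145 − 0.462 × 150 / 145 = 14.5 points, a shift of only 0.5.

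**The case against.** The strongest reply is that few patients are likely to be lost this way. Both arms start the same drug at the same dose, dispensed at the randomisation visit, and dispensing differs only from Week 2. The 2-week arm may also have repeat courses without limit. A patient who dislikes the allocation has more reason to leave later than to refuse the first tablet, and once dosed stays in ITT. Section 5.2.1 does not say when the patient is told, although early disclosure is a fair inference in an open-label trial. This stands: the larger values of k are a stress test, not a forecast.

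The illustration also omits the planned 20% drop-off. Counting drop-outs as failures gives 0.70 × 0.80 × 0.86 = 48.2% against 0.70 × 0.80 × 0.66 = 37.0%, an 11.2-point difference. Eight undosed in one arm then shift it by about 2.1 points (2-week arm) or 2.7 points (8-week arm), instead of 2.6 or 3.4. A single 70% response rate is also applied to both arms despite the different initial durations. Both points affect the size of the bias, not its existence.

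The endpoint is secondary and the primary result does not move, because a never-dosed patient counted as not relieved never enters MITT. That is correct and limits the weight of the point.

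Finally, calling success the only between-arm test in ITT rests on the amended table. Section 12.2.1, which Amendment 1 does not list as changed, still says efficacy endpoints are analysed in ITT, MITT and PP. If that sentence governs, more tests inherit the exclusion, so it does not weaken the concern.

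**Conclusion.** The concern holds. The definition conditions ITT membership on an action taken after the allocation is known, and it applies to the one between-arm test that the amended table assigns to ITT. One-sided losses of 3 to 15 patients out of 150 would move the success difference by about 1 to 7 points, in a direction set by the arm that loses them. Losses of one or two, or equal losses in both arms, move it by less than a point. These sizes rest on an assumed number of undosed patients, on counting them as non-successes, and on the planning rates without drop-off. The effect is confined to a secondary endpoint and is probably modest, but the correction costs so little that it should be made.

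**What to change.** In section 12.1.1 and the synopsis, define ITT as all randomised patients, analysed by allocated regimen. State that a patient who took no dose counts as not relieved and not successful. Keep the one-dose condition for the safety set, whose further requirement of post-dose data (section 12.1.2) stays as it is. Report the number never dosed by arm. If the one-dose set is still wanted, give it another name and use it as a sensitivity analysis. At the same time, bring section 12.2.1 into line with the amended table of section 6.3.1.

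The cost is a few sentences. Success is binary, so no imputation model or new data are needed, and the planned 300 patients are unaffected. If nobody goes undosed, the results are identical. Otherwise the reported success rate falls in the arm concerned, for example by 1.6 points (47.8% to 46.2%) with 5 undosed of 150 in the 2-week arm.
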